OCT is a noninvasive and nondestructive technique that is already recognized as a powerful medical imaging technique

in the field of ophthalmology, in which it is used for imaging the retina. It is a real time, in-vivo technique that has also been used for skin imaging. The instrument uses an echo technique for image collection that is similar in concept to ultrasound, with the exceptions that OCT uses light waves (instead of sound waves) and provides better resolution. OCT allows for noninvasive observation of the skin in a vertical plane up to a depth of ~1 mm, capturing two and three-dimensional images [6]. This allows for visualization of multiple skin structures such as the epidermis, dermis, epidermal junction, and hair follicles. Dynamic OCT allows for the visualization of the microvasculature, along with the skin structures. Previous studies have successfully utilized OCT to image polymeric microneedles in the skin [7-8]. However, OCT has not been used to visualize the micropores formed from metal microneedles, which is the primary focus of the work in our lab group. To date, there are also no studies using OCT to study the microvasculature differences among different racial/ethnic skin types.

In our research program we recently demonstrated that epidermal barrier restoration is slower after microneedle application in darker skin types [9]. We also demonstrated that the use of tristimulus colorimetry as a quantitative measurement of skin color is a better indicator of skin variability than race self-reported by subjects. Using OCT to visualize the skin structures will provide a visual, complementary confirmation of these findings that will augment the impedance calculations that we use as a surrogate measure to determine how long the micropores remain open.

In the current study we will use dynamic OCT and other noninvasive measurements of epidermal properties to comprehensively examine differences in skin properties and micropore closure timeframes after microneedle application in a population of healthy human subjects with racial/ethnic skin.

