## VI. Subjects

VI.1 *How many adult subjects do you expect to consent or enroll for this project?*  
100

VI.2 *What is the age of the youngest adult subject?*  
18.0

VI.3 *What is the age of the oldest adult subject?*  
45.0

VI.4 *What is the percentage of adult male subjects?*  
50

VI.5 *What is the percentage of adult female subjects?*  
50

VI.6 *How many minor subjects do you expect to consent or enroll for this project?*  
0

VI.13 *Describe EACH of your subject populations*

- *Include description of any control group(s)*
- *Specify the Inclusion/Exclusion criteria for EACH group*

There will be no control group for this study.

Inclusion Criteria: Subjects will be healthy men and women between 18 and 45 years of age.

Exclusion Criteria:

- 1) Unable to give consent
- 2) Severe general allergies requiring chronic treatment with steroid or antihistamines
- 3) Previous adverse reaction to microneedle insertion
- 4) History of keloids
- 5) Known allergy or adverse reaction to medical tape/adhesive, or aloe vera
- 6) Any inflammatory diseases of the skin (including but not limited to: psoriasis, atopic dermatitis, and blistering skin disorders)

- 7) Any disease associated with altered immune function (including but not limited to: rheumatoid arthritis, diabetes, lupus, HIV/AIDS)
- 8) Any subject taking medication that impairs the immune system (including but not limited to corticosteroids, TNF inhibitors, monoclonal antibodies, chemotherapy agents)
- 9) Any current malignancy or history of malignancy present at the treatment sites
- 10) Eczema or scaling present at any treatment site; any current inflammation or irritation present at the treatment sites (including but not limited to: rash, inflammation, erythema, edema, blisters)
- 11) Uncontrolled mental illness that would, in the opinion of the investigator, affect the subject's ability to understand or reliably participate in the study

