## **XI. Data Analysis**

**XI.1** *Describe the analysis methods you will use, including, if applicable, the variables you will analyze*  
Paired t-tests will be performed to compare impedance and TEWL measurements pre- and post-micropatch treatment at each site. Influence of skin color and self-reported ethnicity/race on measured parameters will be compared using one-way ANOVA. Micropore closure kinetics will be calculated by modeling the data and calculating a micropore closure half-life. Epidermal thickness, skin roughness, and microvasculature density will be calculated by the OCT software and compared between groups using one-way ANOVA. For all analyses,  $p < 0.05$  will be considered statistically significant. GraphPad Prism Software (GraphPad Software, San Diego, CA) or Microsoft Excel will be used for statistical analyses.

**XI.2** *Provide the rationale or power analysis to support the number of subjects proposed to complete this study.*  
This is a pilot study that does not require a power analysis because data regarding the variability in parameters measured via OCT in racial/ethnic groups is not available. We are targeting 20 subjects per group because this is a reasonable number of subjects for a pilot.

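### Skin colour and self-reported race/ethnicity are tested only one at a time by one-way ANOVA, so the planned analysis cannot say which of the two a difference goes with, nor rank them as indicators

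*Combined protocol and SAP*

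**What the plan says.** Section XI.1 is the only statement of analysis methods, and Section VII.B.11 says that no separate protocol will be submitted. For colour and race/ethnicity it says: "Influence of skin color and self-reported ethnicity/race on measured parameters will be compared using one-way ANOVA". The OCT measures (epidermal thickness, roughness, microvasculature density) are likewise "compared between groups using one-way ANOVA". In every analysis, p below 0.05 "will be considered statistically significant". Section XI.1 names no covariate, two-factor model, regression on both variables or comparison of model fit. It also does not say how colorimeter readings, which are continuous, become ANOVA groups.

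Section I.6 reports from the team's earlier work that "the use of tristimulus colorimetry as a quantitative measurement of skin color is a better indicator of skin variability than race self-reported by subjects", and says that OCT imaging "will provide a visual, complementary confirmation of these findings". Section I.5 aims at closure rates in subjects from different racial/ethnic groups; it lists no comparison of colour with race.

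Both variables are collected on every subject: self-reported race/ethnicity at screening (Section VII.D.26), and colour by colorimetry at each of the nine sites at baseline (Section VII.E.6).

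**The concern.** If self-reported group and measured colour are associated, a test of either one alone also picks up whatever the other contributes. Two significant one-way tests would then fit three explanations equally well: colour matters, group matters for other reasons, or both do. Nothing planned separates these.

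The background makes this more than a technicality. The team already holds that colour describes skin variability better than self-reported race, while the title and aims are framed by race/ethnicity. A reader of the results will ask whether a racial/ethnic difference in closure remains once colour is taken into account, and whether the earlier ranking of the two indicators held up. The analysis as written can answer neither question.

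**Working it through.** **Inputs from the documents.** Alpha is 0.05 (XI.1). Section XI.2 says "We are targeting 20 subjects per group because this is a reasonable number of subjects for a pilot", and Section VI.1 gives a total of 100. 100 / 20 = 5 groups, so five groups are used here. (Section I.4 lists six categories, and 6 × 20 = 120; the number of groups compared is not stated.) There is no planned power or effect size to reproduce: "This is a pilot study that does not require a power analysis".

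**Assumptions, not in the documents.** Group explains a share *a* of colour variance, with *a* = 0, 0.3, 0.5 or 0.7 and group mean colours evenly spaced. The true driver explains a share *r* of outcome variance, with *r* = 0.10 or 0.20. Where colour has to be grouped for an ANOVA, it is cut into quintiles.

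**Tests compared.** One-way ANOVA on group; one-way ANOVA on colour quintiles; and, from one linear model with group plus continuous colour, the partial F-tests of group given colour and of colour given group. There were 2,000 simulated studies per setting, so the standard error is at most √(0.5 × 0.5 / 2000) = 1.1 percentage points.

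**Case A: colour is the only driver.** Percent significant, shown as *r* = 0.10 / *r* = 0.20:

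| *a* | One-way, group | Group given colour | Colour given group |
|---|---|---|---|
| 0 | 5.6 / 5.2 | 5.6 / 4.8 | 88.4 / 99.5 |
| 0.3 | 24.1 / 47.8 | 4.6 / 4.4 | 75.8 / 97.4 |
| 0.5 | 40.2 / 74.1 | 4.9 / 4.8 | 63.2 / 92.8 |
| 0.7 | 55.4 / 90.8 | 5.2 / 5.1 | 42.2 / 74.6 |

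The one-way column can be checked in closed form. Group explains a share *s* = *a* × *r* of outcome variance. The F statistic on 4 and 95 degrees of freedom has noncentrality λ = 100 × *s* / (1 − *s*), and its 5% critical value is 2.467.
- *a* = 0.3, *r* = 0.10: *s* = 0.03, λ = 3.09, rejection 24%.
- *a* = 0.5, *r* = 0.10: *s* = 0.05, λ = 5.26, rejection 40%.
- *a* = 0.7, *r* = 0.20: *s* = 0.14, λ = 16.28, rejection 90%.

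**Case B: group is the only driver, with group effects in the order of the groups' mean colour.**

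| *a* | One-way, colour quintiles | Colour given group | Group given colour |
|---|---|---|---|
| 0 | 5.2 / 5.6 | 5.2 / 4.2 | 73.8 / 98.6 |
| 0.3 | 23.6 / 44.9 | 5.3 / 5.1 | 57.2 / 91.8 |
| 0.5 | 39.0 / 74.1 | 4.8 / 5.0 | 42.1 / 78.4 |
| 0.7 | 54.2 / 90.5 | 5.1 / 5.0 | 24.4 / 51.1 |

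**Case B depends on that ordering.** If group effects are U-shaped across the colour order, the quintile ANOVA is significant in only about 10% to 41% of studies at *a* = 0.5 to 0.7, and a straight-line regression on colour in about 4%.

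**Six groups.** With 6 groups of 17 (*a* = 0.5, *r* = 0.20), the one-way rates are 73% in case A and 72% in case B, so the pattern does not hang on having five groups.

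**The case against.** The strongest objection is that a racial/ethnic difference carried by colour is still a difference between the groups. Section I.5 asks how closure behaves in different racial/ethnic groups, and the unadjusted ANOVA answers that descriptive question correctly. This stands: the 24% to 90% are not false-positive rates for that aim, and the race/ethnicity ANOVA should not be demoted.

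Three stronger readings are tempting, and the documents support none of them.
- A reader might infer that a colour effect *will* be reported as a racial difference, and the reverse. The documents give neither the strength of association nor any effect size. The rate is about 5% with no association, and the reverse case also needs group effects to follow the colour order.
- A reader might infer that the study cannot test whether colour is the better indicator. The limit lies in the stated analysis; both variables are measured on every subject.
- A reader might infer that confirming the ranking is a study aim. It is an earlier result cited in the background and is absent from Section I.5. The promised confirmation is tied in the same sentence to augmenting the impedance calculations, so it may refer mainly to the slower barrier restoration in darker skin.

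The objection from pilot status stands in part. It explains the absence of a power analysis, and it warns that partial tests at this size can miss real effects. It does not supply the missing model when the plan declares significance at 0.05 for all analyses.

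**Conclusion.** The point holds as a gap in the planned analysis. With one factor per test, Section XI.1 can show that outcomes differ by self-reported group or by colour, but not which of the two a difference goes with, and it cannot rank them.

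Under the stated assumptions (5 groups of 20, *a* from 0.3 to 0.7, *r* from 0.10 to 0.20), a one-way race/ethnicity test is significant in about 24% to 90% of studies when only colour matters, against about 5% for group given colour. When only group matters and its effects follow the colour order, the colour-quintile ANOVA gives about the same 24% to 90%; it gives much less under other patterns. The existence of the gap is certain from the text. Its size is not, because it rests on an association and effect sizes that the documents do not report. It is a worthwhile and cheap improvement, and it does not invalidate the planned group comparison.

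**What to change.** In Section XI.1:
1. Keep the one-way race/ethnicity ANOVA, labelled as the unadjusted answer to the aim in Section I.5.
2. For each outcome, add one linear model with self-reported group and the continuous baseline colorimeter reading from the same site.
3. Report the partial F-tests of group given colour and of colour given group, the partial estimates with confidence intervals, and adjusted R-squared for the colour-only, group-only and joint models.
4. State that any claim that colour or race is the better indicator, or that a racial difference is independent of colour, will rest on this model, and that a non-significant partial test will not be read as no effect.

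The cost is wording and some extra analysis; no new data, visits or subjects are needed. The downside is lower power under collinearity. At *a* = 0.5 to 0.7 and *r* = 0.10 to 0.20, power for colour given group is about 42% to 93%, and for group given colour about 24% to 78%. The confidence intervals are there to show how little the data may be able to separate.

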After a subject consents to be in the study, baseline demographic data will be collected from the subject including age, sex assigned at birth, race/ethnicity; information regarding current medical conditions/allergies and medications will also be collected. Specifically, the subject's approximate duration of each condition/allergy, what treatments the subject has received, and approximate severity of the conditions, and a current medication list will be collected. All this information will be collected directly from the subject. The subject's medical record will not be reviewed/abstracted for research data.

After consenting subjects will complete a screening questionnaire either in paper form (attached doc: 202010229\_ScreeningQuestionnaire\_v1) or electronically (attached doc: 202010229\_RedCap\_ConsentScreening\_v1). <https://redcap.icts.uiowa.edu/redcap/surveys/?s=v5UPrZbuFR>

**VII.D.27** *Discuss how much time a potential subject will have to agree to consider participation and whether or not they will be able to discuss the study with family/friends before deciding on participation.*  
There is no limit on the time a potential subject may take to consider participation. The only restriction on time is that the subject will only be allowed to participate if the study is still enrolling subjects when they provide consent. Individuals will

have as much time as needed to discuss with family and friends their participation in the research study.

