## **VII.E. Project Description (E)**

**VII.E.1** *Will subjects be randomized?*  
No

**VII.E.3** *Will any questionnaires, surveys, or written assessments be used to obtain data directly from subjects in this study?*  
Yes

**VII.E.4** *List all questionnaires, surveys, written assessments and ATTACH each one to the application. (NOTE: You are NOT prohibited from attaching copyrighted materials to this application)*  
202010229\_ScreeningQuestionnaire\_v1  
202010229\_PreScreeningQuestionnaire\_v1  
202010229\_DataCollectionSheets\_v1.docx  
202010229\_Emailfollowupscript\_v1.docx

**VII.E.5** *Does this project involve creating any audiotapes, videotapes, or photographs?*  
No

**VII.E.6** *Provide a detailed description in sequential order of the study procedures following the consent process - DO NOT cut and paste from the Consent Document.*

*Describe study populations separately if they will be participating in different procedures - include CONTROL population if*

*applicable.*

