**DESCRIBE:**

- *What subjects will be asked to do/what happens in the study (in sequential order)*
- *The time period over which procedures will occur*
- *The time commitment for the subject for individual visits/procedures*
- *Long-term followup and how it occurs*

Following consent, the subject will fill out a questionnaire collecting information about demographic information age, race/ethnicity, sex assigned at birth, current medications and ongoing medical conditions. The subject will be asked to elaborate on the duration and severity of medical conditions and any treatments received. No medical records will be consulted to obtain or confirm this information. A member of the research team will use this information to screen out subjects meeting any of the exclusion criteria defined in VI.13. Subjects who pass the screening may proceed to the next step described below. Subjects should allow for both in person and electronic consent and screening procedures to take approximately 1 hour; whenever possible, if in person, this will be done on the same day as when the subject starts the study procedures.

On Day 0 (may be the same day as consent is obtained), the subject will sit in the study room at the College of Pharmacy for 30 minutes prior to any procedures. This allows the subject's skin to acclimate to the ambient environment in the study room (temperature, humidity). During this 30 minute period, the study team member will verify screening information collected through the online survey with the participant, as well as measure height, weight, calculate BMI. If screening information is verified correct from participant research procedures will continue as planned. (This procedure will be followed as do to scheduling constraints it is possible that some time has passed from when the subject consented to when they are scheduled to complete their study procedures. Verifying this information will help us determine if their original answers remain accurate and their eligibility remains.) If participants answers indicate that they are actually ineligible to continue their participation no further procedure will take place and the subject will be removed from the study. Following this acclimation, the researcher will identify and mark with a pen 3 sites each on the upper arm, forearm, and the palm. Hair may be clipped (but not shaved) at any sites if necessary. Noninvasive baseline measurements will be taken at each of the 9 sites as follows:

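### Race/ethnicity and skin-colour comparisons use an unadjusted one-way ANOVA although sex, age and BMI are collected, so a group difference can partly reflect the mix of these factors

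*Combined protocol and SAP*

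**What the plan says.** XI.1 gives one method for comparing subjects with each other. For the general outcomes, "Influence of skin color and self-reported ethnicity/race on measured parameters will be compared using one-way ANOVA". The OCT outcomes (epidermal thickness, roughness, microvasculature density) are likewise "compared between groups using one-way ANOVA". A p-value below 0.05 "will be considered statistically significant" for all analyses. No covariate, regression, stratification or matching is named anywhere.

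The relevant design facts are these:

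- VII.E.1 asks "Will subjects be randomized" and the answer is no. Race/ethnicity is self-identified (I.4).
- VII.D.26: "baseline demographic data will be collected from the subject including age, sex assigned at birth, race/ethnicity". On Day 0 the team will verify the screening answers "as well as measure height, weight, calculate BMI" (VII.E.6).
- VI.13: "Subjects will be healthy men and women between 18 and 45 years of age". No age balance between groups is described.
- VI.4 asks "What is the percentage of adult male subjects" and the answer is 50. This is a figure for the whole study, not for each group.
- VII.D.29 plans targeted advertisements to reach specific populations. Nothing there concerns sex, age or BMI.

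**The concern.** A one-way ANOVA compares raw group means. If one group happens to include more women, or older or heavier subjects, and the outcome varies with that factor, the shift appears as a racial or ethnic difference. The study's title and first aim (I.5) concern differences between such groups, and XI.1 speaks of influence and of significance, so readers will take the result as more than a description of who enrolled. The plan already collects what is needed to check this and does not use it.

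There is also a cost in precision. Variation due to sex or age stays in the error term and makes real group differences harder to see.

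**Working it through.** **The plan's own figure.** XI.2 targets 20 per group and VI.1 expects 100 subjects; 100 / 20 = 5 groups. I.4 lists six categories (6 × 20 = 120), so five groups is an assumption here. No effect size, SD or power is stated, so there is no sample-size calculation to reproduce.

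**Assumed inputs (not in the documents).** Five groups of 20; no true group effect; sex effect 0.5 or 1 SD; sex share rising evenly across groups from 30% to 70%, or from 40% to 60%. Where a second covariate (age or BMI) is included, its group means run from −0.5 to +0.5 SD with slope 0.3.

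**Shift between the two extreme groups.** Spurious difference = (difference in sex share × sex effect) ± (slope × difference in covariate means).

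- Sex alone, 30% v 70%: 0.4 × 0.5 = 0.20 SD; 0.4 × 1 = 0.40 SD.
- Second covariate alone: 0.3 × 1.0 = 0.30 SD.
- Same direction: 0.20 + 0.30 = 0.50 SD; 0.40 + 0.30 = 0.70 SD.
- Opposed: 0.30 − 0.20 = 0.10 SD; 0.40 − 0.30 = 0.10 SD.

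**Simulated rejection rate of the unadjusted ANOVA at 0.05.**

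| Setting | Sex effect 0.5 SD | Sex effect 1 SD |
|---|---|---|
| Sex only, fixed 40–60% mix | 4.4% | 3.0% |
| Sex only, fixed 30–70% mix | about 6% | about 9% |
| Sex only, counts random around 30–70% | 7–8% | 13–14% |
| Fixed 30–70% plus second covariate, same direction | 20% | 28–29% |
| Random 30–70% plus second covariate, same direction | 21–23% | 35–36% |
| As the row above, covariate slope 0.1 | 10% | 20% |
| As the 21–23% / 35–36% row, covariate spread halved | 12% | 23% |
| 30–70% plus second covariate, opposed | about 5% | 3–6% |

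The model adjusted for the imbalanced covariates rejects about 5% of the time (range 4–6%) in every setting. A wider fixed sex mix of 20–80% gives 9.4% and 23.0% from sex alone.

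Rates below 5% in the first row are the precision cost. With exactly 10 women in each group the unadjusted test rejects 4.0% (0.5 SD) and 1.8% (1 SD), because the sex variation inflates its error term.

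**Precision.** With noncentrality λ = f²N / (1 − R²) and an assumed f = 0.36, f²N = 0.1296 × 100 = 12.96.

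- R² = 0: λ = 12.96, power 81%.
- R² = 0.10: λ = 14.40, power 86%.
- R² = 0.20: λ = 16.20, power 90%.
- R² = 0.30: λ = 18.51, power 94%.

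**How uneven could the sex mix be?** With a true 50% share in every group of 20, the expected range in female share across five groups is about 26 percentage points, and the probability of 30 points or more is 0.41. Chance imbalance of this kind does not raise the long-run error rate by itself, but it does shift the means in the one sample that is observed.

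**The case against.** The strongest reply is that this is a pilot with a descriptive purpose. The raw difference between recruited groups is a legitimate summary, and it is a false positive only if the adjusted difference is what one wants. This stands as a reason to keep the unadjusted result. It does not remove the point, because XI.1 attaches a significance threshold to the comparison and describes it as influence.

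Second, the documents give no effect of sex, age or BMI on closure, TEWL or OCT measures, and no evidence of imbalance. The 18–45 age range and the exclusions narrow some of the scope for confounding. This also stands, and it limits how far the size can be pressed. A reader might infer that the planned ANOVA has a false-positive rate of 20–36%. The documents do not support that. Under the 30–70% mix those figures require a second covariate imbalanced in the same direction as sex and acting the same way on the outcome. Reverse the direction and the inflation disappears.

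A reader might also take the lack of randomisation as the fault. It is not, since race and ethnicity cannot be assigned. What is missing is adjustment or balancing.

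The statement in VII.D.29 that participants serve as their own controls does not answer the point. It applies to treated and control sites within a person, not to comparisons between people.

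**Conclusion.** The point holds as a weakness in the choice of analysis. The planned between-group test cannot separate group from sex, age or BMI, and the plan neither balances these within groups nor uses them. The documents do not show that any particular result will be confounded; they show only that the plan could not tell.

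The illustrated size runs from no inflation (mild or opposed imbalance), through about 6–9% for sex alone at a fixed 30–70% mix, to 20–36% in the same-direction worst case, against a nominal 5%. All of this rests on the assumed effects and mixes above. The power gain from 81% to 86–94% likewise rests on an assumed f and on covariates explaining 10–30% of the variance. What does not depend on those assumptions is that the data are already collected and adjusting for them costs very little. The change should be made before the data are analysed.

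**What to change.** Amend XI.1 as follows:

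1. For each outcome, make the between-group analysis a linear model (ANCOVA) with race/ethnicity group, sex and age.
2. Fit skin colour in a separate model as a continuous colorimetry term with the same covariates. The plan gives no cut-points from which colour groups for an ANOVA could be formed.
3. Report the unadjusted one-way ANOVA beside the adjusted result as the description of the recruited groups.
4. Add BMI as a sensitivity analysis rather than to the main model, because it may lie on the pathway between group and outcome.

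The cost is small. With five groups of 20 there are 100 − 5 = 95 error degrees of freedom, falling to 93 with sex and age and to 92 with BMI. No new measurement is needed and the analysis work grows slightly. XI.1 names GraphPad Prism or Excel, so the team should confirm that the tool it uses can fit these models.

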#### **I.5**

##### ***Specify your research question(s), study aims or hypotheses (do not indicate "see protocol")***

This study aims to visualize micropores and measure micropore closure rates following micropatch application at 3 anatomical sites in subjects from different racial/ethnic groups. Another study aim is to quantify differences in skin structure and blood flow using OCT imaging. We hypothesize that OCT images of micropores in the skin will provide a complementary approach to calculating micropore lifetime, when combined with impedance calculations.

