**VII.D.29 *Provide a description of the enrollment and consent process for adult subjects***

- **Describe each study population separately including control population**
- **Include when recruitment and consent materials are used**
- **Use 3rd person active voice “The Principal Investigator will identify subjects. For example, the principal investigator will identify potential subjects, the study coordinator will discuss the study with subjects over the telephone and schedule the first study visit, etc...”**
- **Describe the steps that will be taken by the research team to minimize the possibility of coercion or undue influence during the consent process**

Participants in this study will be normal healthy individuals aged 18-45. All participants will act as their own controls.

This study will be advertised through the University of Iowa campus-wide email system and through the University of Iowa Health Care “Noon News,” a daily announcement flier for community and faculty members within the UIHC. Advertisements for this study have been created so that specific subject populations may be better reached via targeted advertisements, in order to meet our enrollment goals. (attached docs: 202010229\_MassEmail\_v1; 202010229\_NoonNews\_v1)

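### XI.1 specifies no comparison of locations and no group-by-location analysis, although the aim covers closure at three locations measured in every subject

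*Combined protocol and SAP*

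**What the plan says.** Section I.5 gives the aim as to "measure micropore closure rates following micropatch application at 3 anatomical sites in subjects from different racial/ethnic groups". Group and location stand side by side in that sentence.

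The procedures in VII.E.6 make location a within-subject factor: "the researcher will identify and mark with a pen 3 sites each on the upper arm, forearm, and the palm". The same three conditions are used at each location: micropatch with covering, micropatch without covering, and covering alone. VII.D.29 adds: "All participants will act as their own controls".

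XI.1 is the only analysis text, since VII.B.11 states that no separate protocol exists. It contains:

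- For the change after treatment, tests of before against after, one site at a time, on impedance and water loss.
- For group and colour effects: "Influence of skin color and self-reported ethnicity/race on measured parameters will be compared using one-way ANOVA".
- For the closure endpoint: "Micropore closure kinetics will be calculated by modeling the data and calculating a micropore closure half-life".
- For the OCT measures, values "compared between groups using one-way ANOVA".

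A 5% significance threshold applies to every analysis. XI.1 mentions no location factor, group-by-location term or repeated-measures model, and it does not say whether the ANOVAs are run separately by location or on pooled sites.

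**The concern.** A one-way ANOVA carries one factor. If that factor is race/ethnicity or colour, the test says nothing about location and nothing about whether the group difference changes with location. The pre/post t-tests show whether a site changed after treatment, which is a different question again.

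This does not depend on how the ANOVAs are run. Run by location, they yield three p-values and no test of the difference between them. Run on pooled sites, they absorb location into the error and ignore the correlation within a subject. Reducing the data to one value per subject per location would not supply the missing terms either.

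What is at stake is how the location results can be interpreted. With three separate tests and about 20 subjects per group, a group difference can reach significance at one location and miss it at another by chance alone. A difference in significance is not a test of a difference in effect.

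**Working it through.** **Inputs from the documents.** Total enrolment 100 (VI.1); 20 per group (XI.2); three locations per subject (VII.E.6); threshold 0.05 (XI.1). The plan's own numbers fit five groups: 5 × 20 = 100. Section I.4 lists six self-identification options, and 6 × 20 = 120 does not match. The number of analysis groups is not stated, so five is an assumption here.

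**Assumed, because the documents give no effect size or variability.** The same group effect at all three locations, Cohen's f of 0, 0.25, 0.35 or 0.40, and within-subject correlation ρ between locations of 0 to 0.7.

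**Step 1: closed form for independent tests.** If each of three tests has power p, the chance that one or two but not all three are significant is 1 − p³ − (1 − p)³. This gives 0.14 at p = 0.05, 0.75 at p = 0.5, 0.48 at p = 0.8 and 0.27 at p = 0.9. The peak is at 50% power, so a figure quoted only there is a worst case.

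**Step 2: simulation of the planned test.** A one-way ANOVA at each location, five groups of 20, 6,000 runs per scenario. Chance of a mixed pattern when the effect is truly identical everywhere:

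| f (power per location) | ρ = 0 | ρ = 0.3 | ρ = 0.5 | ρ = 0.7 |
|---|---|---|---|---|
| 0 (about 5%) | 14.9% | 14.2% | 12.9% | 10.7% |
| 0.25 (about 47%) | 74.4% | 64.0% | 53.8% | 41.9% |
| 0.35 (about 79%) | 49.7% | 43.4% | 35.5% | 28.2% |
| 0.40 (about 89%) | 27.7% | 25.7% | 21.8% | 18.1% |

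The ρ = 0 column agrees with Step 1. With six groups of 16, the range for f 0.25–0.40 is 23–72%; with six groups of 20 it is 13–74%.

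**Step 3: the direct test on the same data.** A repeated-measures group-by-location F test was significant in 4.5–5.6% of runs across the five-group scenarios, close to its nominal 5%.

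**Step 4: what the design can estimate.** Standard errors in units of the outcome SD, at ρ = 0.5:

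- Location contrast, 100 subjects: √(2(1 − 0.5)/100) = 0.10.
- Group contrast at one location, 20 v 20: √(2/20) = 0.32.
- Group-by-location contrast, two groups of 20 and two locations: √(2 × 2(1 − 0.5)/20) = 0.32.

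For a true 0.5 SD difference in group effect between two locations, 0.5/0.316 = 1.58, and the power is about Φ(1.58 − 1.96) = 35%. The main location contrast is therefore precise, but the interaction is not.

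**The case against.** **No location comparison is promised.** I.5 can be read as naming the places where closure is measured. The title, background, hypothesis and stated benefits concern racial/ethnic or colour differences and OCT as a complement to impedance. This stands as far as it goes: the location question is a reasonable reading of the aim, not its wording. But if locations are not to be compared, XI.1 should say so.

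**A reader might infer that the investigators intend to present significance on the forearm but not the palm as a location difference.** The documents do not support that. No section states such an inference or says that the ANOVAs are run by location; in XI.1, testing at each site is stated only for the pre/post t-tests. What can be said is that the plan offers no other basis for a location statement.

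**A reader might also infer from the 0.10 SD figure that the interaction can be estimated well.** It cannot. That figure belongs to the overall location contrast. Making location-specific reporting depend on a significant interaction would therefore be unsound.

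**This is a pilot without a power analysis.** XI.2 says so: "We are targeting 20 subjects per group because this is a reasonable number of subjects for a pilot". That excuses low power. It does not excuse leaving a within-subject factor out of the analysis while applying a 5% threshold throughout.

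**Conclusion.** The gap is real. XI.1 contains no analysis that compares locations or tests whether a group difference depends on location, and no other section fills it. The consequence is a risk of misreading, not a planned error. The size of that risk depends on the unknown true effect: it is highest when power at each location is near one half and falls as power rises. The 18–74% range rests on an identical effect at every location and on the assumed group number, effect sizes and correlations. It shows how little separate p-values would say about location; it does not predict this trial's result. The point merits a change to XI.1 but does not undermine the study.

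**What to change.** In XI.1, analyse log half-life and the baseline OCT measures with a repeated-measures or mixed model containing group, location, group-by-location and a subject random effect. For half-life, add an occlusion term, because each location has one covered and one uncovered micropatch site and so yields two half-lives. Enter colour as a site-level covariate, since it is measured at each site and can vary within a subject.

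Report the location contrasts, the location-specific group effects and the interaction, each with a confidence interval and labelled exploratory. State two rules of interpretation: a location difference will not be inferred from differing p-values, and a non-significant interaction will not be taken as evidence of equal effects. If the investigators do not want to compare locations, the minimum is a sentence saying that they will be described only and that no location-specific group claims will be made.

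The cost is somewhat more analysis work, including a check that the software named in XI.1 can fit the model, and fewer location-specific claims. No extra subjects, visits or measurements are needed.
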